8.2.3 Concomitant Medication and Treatment

Concomitant medication prescribed for concomitant diseases and treatment for mM at the beginning of the observation period or introduced during the observation period will be documented in the CRF from start of therapy with vemurafenib / cobimetinib until discontinuation of the treatment if applicable.

8.2.4 Dosage, Administration, and Compliance

Dosing and treatment duration of any studied medicinal products collected as parts of this non-interventional study are at the discretion of the physician in accordance with local clinical practice and local labeling.

8.3 VARIABLES

8.3.1 Primary Variable

The primary variable for this study is as follows:

- OS: Time interval between start of treatment and date of death for any cause

8.3.2 Secondary Variables

The secondary variables for this study are as follows:

- PFS
- ORR
- Time to CNS relapse / development of cerebral metastases
- Description of previous therapies and therapies after cobimetinib / vemurafenib discontinuation
- Description of Radiotherapy
- Description of Concomitant medication
- QoL

8.3.3 Primary Safety Variables

The primary safety variables for this study are as follows:

- Total adverse events
- Serious adverse events
- \geq grade 3 adverse events
- Adverse events leading to treatment discontinuation
- Adverse events of special interest

8.4 DATA SOURCES

8.4.1 Collection of Data on the CRF

Patients' data will be recorded on eCRFs. The degree of detail and completeness of data collected is dependent on local clinical practice. Data from patient notes should be entered on the eCRF as soon as they become available.

8.4.2 Data Collected during the Observation Period

During therapy with a combination of vemurafenib and cobimetinib, laboratory assessments are routinely performed in accordance with current guidelines and local standard of care. When performed during the observational period, available results from the range of assessments described below will be documented on the CRF. Most data will be documented around the point in time or period during the treatment period when the respective assessments are usually performed according to standard of care. The proposed assessments and suggested timings for assessments in the protocol/observational plan are not mandatory. It is up to the treating physician to perform and document the assessments as performed in the real clinical setting.

At baseline the following items should be documented:

- Acceptance of inclusion / exclusion criteria
- Demographic data include age, sex, and self-reported race / ethnicity
- ECOG performance status
- Elevated LDH level within 1 month before cobimetinib / vemurafenib initiation
- Medical history including significant diseases within the previous 3 years, major surgeries.
- Melanoma history (including information on primary mM [date of diagnosis, histologic type, site, Breslow's thickness], BRAF mutation status, date of first diagnosis AJCC stage IIIC unresectable or stage IV, current AJCC stage; prior adjuvant and palliative therapies for melanoma, number of extracranial metastatic sites at baseline, presence of liver metastasis at baseline, in case of brain metastasis: date of first diagnosis of brain metastasis, prior local treatment for brain metastasis, number of brain metastases, largest diameter, symptomatic/asymptomatic brain metastasis, leptomeningeal disease, concomitant medication for brain metastases [i.e. steroids, anticonvulsants])
- Concomitant medication
- Start date of therapy with cobimetinib / vemurafenib

During observation period the following items should be documented (if applicable):

- Start and end date of treatment interruption (if appl.)
- Start and end date of dose modification (if appl.)
- Information on dose modification (if appl.). dosage and dosing schedule of cobimetinib / vemurafenib
- Reason for dose modification / treatment interruption (if appl.)
- Concomitant local treatment for brain metastasis (if appl.) Concomitant local treatment for brain metastasis (including type of treatment [i.e. surgery, radiotherapy], type of radiotherapy [i.e. whole brain radiotherapy, whole brain radiotherapy with boost, stereotactic radiotherapy], total dose and fraction of radiotherapy, number of metastases treated, steroid use prophylactic or therapeutic)
- Concomitant medication
- Tumor Response (CR, PR, SD, PD) according to clinical practice
- Elevated LDH level during therapy / follow up
- Date of disease progression
- Date of death
- Stop date of therapy with cobimetinib / vemurafenib
- Reason for Discontinuation: PD, AE/SAE, patient's wish, response, physician's decision
- AEs, SAE, AEs of interest, Pregnancies

In the routine care setting, patients are seen regularly by their treating physicians either for treatment or for regular assessment after treatment. Thus, no study-specific visits or evaluations are required by this protocol.

Please see Appendix 2 for the data collection overview (as per standard of care) during the treatment period.

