Malignant melanoma is the third most common disease to develop brain metastases. Up to 11% of all patients with cerebral metastases are diagnosed with mM (12). Around 10 percent of initially diagnosed mM patients present with brain metastases (13, 14). Over the course of disease, the risk for brain metastasis increases. In a phase III trial recruiting patients without brain metastases comparing dacarbazine and temozolomide, 20 – 30% of patients had developed brain metastases at 12 months increasing to 30 - 40% after 3 years (15). Data from the central registry mM shows around 30 percent of patients develops brain metastasis (16). Autopsy series have reported up to 75% of mM patients having brain metastases (17).

Before the advent of targeted therapies, OS for patients with brain metastases was 4.3 months (18). Melanoma patients treated with single agent BRAFi have an OS of 4.3 to 13 months, but the outcome seems to be inferior to patients without brain metastases (19). In a pilot study, Dummer et al. (20) treated patients with BRAF V600 mutation–positive metastatic mM and previously treated, unresectable brain metastases, requiring corticosteroids for symptom control. Intracranial ORR was 16% with a median duration of response in the brain of 4.4 (2.1–4.6) months. Median OS was 5.3 months, and median PFS in the brain was 4.3 months.

According to current treatment guidelines in Germany (23), first line treatment for BRAF V600-mutated mM should be either combined BRAFi/MEKi or PD-1 Ab therapy or combined PD-1/CTLA-4 Ab therapy.

In patients with brain metastases, therapy guidelines differentiate between multiple, symptomatic brain metastases as opposed to limited brain metastasis. For the latter, surgery or stereotactic radiotherapy is recommended. For multiple, symptomatic brain metastases palliative whole brain radiotherapy is recommended, if life expectancy exceeds three months. To date, no guidance on adjuvant radiotherapy after R0-resection of brain metastases is given.

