7.2 OBJECTIVES

The primary objective for this study is as follows:

- to estimate OS according to cohorts with cerebral and without cerebral metastases (investigator assessed)

The secondary objectives for this study are as follows:

- to estimate intermediate endpoints, including:
 - PFS (investigator assessed)
 - ORR (CR + PR) (investigator assessed)
 - Intracranial ORR (iORR)
 - Extracranial ORR (eORR)
 - Time to CNS relapse in cohort with cerebral metastases / development of cerebral metastases in cohort with solely extracerebral metastases (investigator

assessed)

- to describe clinical characteristics of patients overall, and according to both cohorts (i.e. demographic data, medical history, information on primary mM, ECOG performance status, serum LDH at baseline, number of extracranial metastatic sites at baseline; in case of brain metastasis: number of brain metastases, largest diameter, symptomatic/asymptomatic brain metastasis, leptomeningeal disease, concomitant therapy for brain metastasis)
- to describe utilization of cobimetinib / vemurafenib (type and number of previous adjuvant and palliative treatments, dosing schedules, treatment beyond progression, reason for discontinuation, subsequent therapies and concomitant medication)
- to describe utilization of cobimetinib / vemurafenib and treatment for brain metastasis (prior local treatment for brain metastases, concomitant radiotherapy or surgery, type of radiotherapy, steroid use prophylactic or therapeutic, use of anticonvulsiva)
- to describe patient reported outcome using the EORTC QLQ-C30 questionnaire

Safety Objectives

The safety objectives for this study are as follows:

The incidence of all adverse events (AEs) and serious adverse events (SAEs) in cobimetinib / vemurafenib treated patients.

- All protocol-specified adverse events (AEs) described in this section will be reported and graded according to the National Cancer Institute Common Terminology Criteria for Adverse Events version 4 (CTCAE v4.03).
- Incidence and outcomes of serious and non-serious AEs of interest (i.e., those AEs identified by Genentech/Roche as potential or known risks of cobimetinib and/or vemurafenib use)
- These AEs of interest for the combination of vemurafenib and cobimetinib include the following:
 - Any grade serous retinopathy
 - Any grade retinal vein occlusion
 - Grade \geq 2 left ventricular dysfunction

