8.7.1 Safety Analyses

All patients who received at least once cobimetinib and vemurafenib will be part of the safety population which is identical to the core analysis population.

The analysis of safety outcomes/variables is based on the incidence and severity of all AEs, SAEs, AEs with NCI CTCAE version {4.0}.

Safety will be assessed through summaries of adverse events. Descriptive statistics will be used to summarize all safety data. Adverse event data will be reported in listings and presented in frequency tables by Medical Dictionary for Regulatory Affairs (MedDRA) terms. All adverse events occurring after treatment will be summarized. Summaries of adverse events by grade, seriousness, and relationship to study treatment will be presented, as well as summaries of adverse events leading to death or to premature withdrawal from study treatment. Serious adverse events, including deaths, will be listed separately and summarized.

8.7.2 Effectiveness Analyses Effectiveness analyses will be based on all enrolled patients according to both defined cohorts:

Patients with:

Cohort A: patients with AJCC stage IIIC unresectable and stage IVA, B, C mM without cerebral metastases

or

Cohort B: patients with AJCC stage IVC and cerebral metastases

All effectiveness and variables documented in this study will be analyzed by means of descriptive analyses.

Continuous data will be summarized using mean, standard deviation, median, minimum and maximum. Categorical variables will be expressed as absolute and relative number and 95% CI. Kaplan-Meier estimates and Cox-regression will be used to model data on time to disease progression and OS.

All efficacy analyses will be performed separately for both groups.

The primary variable OS is defined as time interval from study start to death for any cause. Patients who have not died will be censored at the last date the patient was known to be alive. A 95% confidence interval will be calculated for the median overall survival.

PFS is defined as the interval between the start date of treatment and the date of progression or death for any cause, whichever comes first. Patients who have neither progressed nor died will be censored on the date of last evaluable tumor assessment.

Patients who had no post-baseline assessments and did not have an event will be censored OR is defined as a complete or a partial response documentation on the basis of investigator assessment.

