Appendix 2 Data Collection Overview (as per Standard of Care)

Data Collection (available data will be collected; no additional diagnostic or monitoring procedures shall be applied to the patients outside of routine clinical practice)	Baseline	Data Collected during Observational Period	End of Treatment	Data Collected during Follow-Up
Inclusion/exclusion criteria ^a	x			
Demographic data ^b	x			
ECOG PS	x	x	x	x
Elevated LDH level within 1 month before cobimetinib / vemurafenib initiation	x			
Quality of Life (EORTC QLQ C30)	x	x	x	
Medical history ^c	x			
Melanoma history ^d	x			
Concomitant medication	x	x	x	
Start date of therapy with cobimetinib / vemurafenib	x			
Start and end date of treatment interruption (if appl.)		x	x	
Start and end date of dose modification (if appl.)		x	x	
Information on dose modification ^e (if appl.)		x	x	
Reason for dose modification / treatment interruption (if appl.)		x	x	
Concomitant local treatment for brain metastasis ^f (if appl.)		x	x	
Tumor Response (CR, PR, SD, PD) ^g		x	x	
Elevated LDH level during therapy / follow up		x	x	x
Date of disease progression		x	x	
Stop date of therapy with cobimetinib / vemurafenib		x	x	
Reason for Discontinuation ^h		x	x	
AEs, SAE, AEs of interest, Pregnancies		x	x	x
Therapy following cobimetinib / vemurafenib (if appl.)				x
Tumor Response to following therapy (CR, PR, SD, PD) ^g				x
Date of death		x	x	x
Reason for death ⁱ		x	x	x

- ^a Inclusion criteria: Date of informed consent, age \geq 18 years, date of histologically confirmed malignant melanoma, AJCC stage IIIC unresectable or IV, date of positive BRAF V600 mutation analysis; exclusion criteria: no previous with BRAF- and/or MEK inhibitors prior to study entry, no Hypersensitivity to the active substances or to any of the excipients listed in appendix 4
- ^b Demographic data include age, sex, and self-reported race/ethnicity.
- ^c Medical history including significant diseases within the previous 3 years, major surgeries.

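### The protocol defines Cohort A by absence of cerebral metastases but does not list whether, when or how the brain was imaged, so scan-negative and never-scanned patients cannot be told apart

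*Protocol*

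**What the plan says.** The primary objective in section 7.2 is "to estimate OS according to cohorts with cerebral and without cerebral metastases". Section 8.7.2 defines the first group by a negative: "Cohort A: patients with AJCC stage IIIC unresectable and stage IVA, B, C mM without cerebral metastases". Neither section, nor 8.1 or 8.5, says how absence of cerebral metastases is established.

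The baseline list in section 8.4.2 conditions every brain item on a known metastasis: "in case of brain metastasis: date of first diagnosis of brain metastasis, prior local treatment for brain metastasis, number of brain metastases". Footnote d of Appendix 2 does the same. During observation the tumour items are "Tumor Response (CR, PR, SD, PD) according to clinical practice", a date of disease progression, and local treatment of brain metastases where it applies. I found no item in section 8.4.2 or in any column of Appendix 2 for brain imaging done or not done, its date or its method.

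Imaging cannot be imposed. Section 8.4.2 states: "The proposed assessments and suggested timings for assessments in the protocol/observational plan are not mandatory". Appendix 2 adds: "available data will be collected; no additional diagnostic or monitoring procedures shall be applied to the patients outside of routine clinical practice". That last sentence forbids extra procedures but provides for recording what is available.

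Section 8.9 names information bias, measurement error and missing data as limitations and promises a sensitivity analysis for bias. Section 8.7 leaves assignment to populations to a data review meeting before database closure.

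**The concern.** A negative brain status means something different in a patient scanned shortly before first dose and in one never scanned. With the listed items the two records are identical. Neither the data review meeting nor the promised sensitivity analysis can separate them from the study database.

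Three results depend on this:

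- **Development of cerebral metastases in Cohort A.** Disease present but undiagnosed at entry appears as a new event at the first scan. Without scan dates, the timing of events also cannot be separated from the timing of scans.
- **OS in Cohort A.** Undiagnosed patients would pull the estimate towards that of Cohort B.
- **Comparability of sites.** Assessments are left to the physician at about 40 centres, so scanning practice may differ without leaving a trace.

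This is not a detail for the analysis plan, because an analysis plan cannot use a variable that was not collected.

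**Working it through.** **Inputs from the protocol.** Section 8.5: Cohort A n = 157, assumed median OS 25 months, 95% CI [19; 31]; Cohort B n = 68, assumed median 12 months, 95% CI [8.5; 15.5]. Section 6.1: 20-30% with brain metastases at 12 months in a trial that enrolled patients without them. Section 8.7.2: time to CNS relapse counts death from any cause as an event.

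**Assumptions, not in the documents.** A share q of Cohort A has undiagnosed brain metastases at entry and has Cohort B's survival. The 25-month median holds for the remaining patients. Survival is exponential.

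**Step 1: the plan's own interval.** Large-sample non-parametric CI for a median: m ± 1.96·m/(ln 2·√n).

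- n = 157: 25 ± 1.96·25/(0.693·12.53) = 25 ± 5.64, giving [19.4; 30.6].
- n = 141 (after 10% dropout): [19.05; 30.95].

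The stated [19; 31] reproduces.

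**Step 2: effect on Cohort A OS.** Solve (1−q)·2^(−t/25) + q·2^(−t/12) = 0.5 for t. The CI is t ± 1.96·0.5/(f(t)·√157), where f is the mixture density.

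| q | patients of 157 | median OS (months) | 95% CI |
|---|---|---|---|
| 0 | 0 | 25.0 | [19.4; 30.6] |
| 5% | 8 | 24.1 | [18.6; 29.6] |
| 10% | 16 | 23.1 | [17.8; 28.5] |
| 20% | 31 | 21.4 | [16.4; 26.4] |
| 25% | 39 | 20.6 | [15.7; 25.4] |
| 30% | 47 | 19.8 | [15.1; 24.5] |

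The sizing aim in section 8.5 is that Cohort A's lower limit stays clear of Cohort B's upper limit. Against the stated 15.5 months it fails at about 25-30%. The Step 1 formula gives Cohort B [7.9; 16.1] rather than [8.5; 15.5]. Against 16.1 the crossing would lie between 20% and 25%, still well above 5-10%.

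**Step 3: effect on the CNS endpoint.** I take the composite definition in section 8.7.2 to apply to development of cerebral metastases in Cohort A as well.

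- Deaths by 12 months: 1 − 2^(−12/25) = 1 − 0.717 = 28.3%.
- With 25% brain metastases by 12 months (midpoint of 20-30%) and independence: 1 − 0.717·0.75 = 46.2% with an event.
- Share due to disease present at entry: 5/46.2 = 11% and 10/46.2 = 22%.
- With 20% brain metastases: 1 − 0.717·0.80 = 42.6%, share 12-23%. With 30%: 1 − 0.717·0.70 = 49.8%, share 10-20%.

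These shares assume that all pre-existing disease is found within 12 months and is included in the 20-30%. That range comes from a trial of dacarbazine and temozolomide, so it is only a rough guide here.

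**The case against.** **A legitimate real-world definition.** The target population is patients in routine care, so brain status as known to the treating physician is a defensible cohort definition. This stands, and it is why Cohort A should stay as defined. It does not remove the need to know how that status was reached.

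**Silent disease at entry.** A reader might infer from section 6.1 that undiagnosed brain metastases at entry are likely. The figures do not show that. The 20-30% is later incidence in patients enrolled without brain metastases. The sentence "Autopsy series have reported up to 75% of mM patients having brain metastases" describes disease at death. The figure nearest to entry, about 10%, counts patients who present with diagnosed brain metastases. No section gives a rate of occult disease or of routine imaging.

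**The primary comparison.** A reader might also infer that the OS result by cohort is compromised. Step 2 does not support that at plausible shares. The analysis is also descriptive, without hypothesis tests, and the cohorts are analysed separately.

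**The CNS endpoint.** Dividing 5-10% by 25% would suggest that a fifth to two fifths of 12-month events are affected. That leaves out deaths, which section 8.7.2 counts as events.

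**Later recovery.** Sites keep records for at least 15 years (section 8.8.3), source data are verified (section 8.6.3), and queries before closure remain possible. So it would go too far to say that the problem could never be found. None of these routes supplies the field prospectively, however. The melanoma history is introduced as a list of what is included, and the eCRF is not shown, so an imaging field might exist there. The protocol does not provide for one.

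**Conclusion.** The point holds as a gap in data capture. Under the listed items, the absence of cerebral metastases that defines Cohort A cannot be checked, and the sensitivity analysis promised in section 8.9 has no variable to work with on this source of bias.

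The main exposure is the secondary CNS endpoint: roughly 11-22% of 12-month composite events if 5-10% of Cohort A had disease at entry, on the assumptions in Step 3. The effect on primary OS is probably small. At 5-10% the median moves by 0.9-1.9 months, well inside the stated [19; 31]. The misclassified share is an assumption throughout. The documents support an uncheckable cohort definition, not a demonstrated failure of the primary estimate. I rate it a cheap and worthwhile improvement.

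**What to change.** Add to the baseline list in section 8.4.2 and to Appendix 2, for all patients and from existing records only: brain imaging before start of cobimetinib / vemurafenib (yes / no / unknown), date of the last examination, and method (MRI or CT). Add to the observation, end-of-treatment and follow-up columns the date and method of each routine brain imaging, where available.

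Keep Cohort A as defined for the main analysis. Name the imaging-confirmed subset of Cohort A as part of the sensitivity analysis in section 8.9, for OS and for time to cerebral metastases. The imaging window that defines the subset can be set in the analysis plan.

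The cost is a few eCRF fields, a little more data entry per patient, and one sensitivity table. No scan is required, so the study stays non-interventional and within the rule in Appendix 2.

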Around 10 percent of initially diagnosed mM patients present with brain metastases (13, 14). Over the course of disease, the risk for brain metastasis increases. In a phase III trial recruiting patients without brain metastases comparing dacarbazine and temozolomide, 20 – 30% of patients had developed brain metastases at 12 months increasing to 30 - 40% after 3 years (15). Data from the central registry malignant melanoma shows around 30 percent of patients develops brain metastasis (BM) (16). Autopsy series have reported up to 75% of melanoma patients having brain metastases (17).

Before the advent of targeted therapies, OS for patients with brain metastases was about 4 months (20). Melanoma patients treated with single agent BRAF inhibitors have an OS ranging between 4.3 to 13 months (21, 22). In a pilot study, Dummer et al. (20) treated patients with BRAF V600 mutation–positive metastatic mM and previously treated, nonresectable BM, requiring corticosteroids for symptom control using vemurafenib monotherapy. Intracranial ORR was 16% with a median duration of response in the brain of 4.4 (2.1–4.6) months. Median OS was 5.3 months, and median PFS in the brain was 4.3 months.

Commonly, mM patients with central nervous system (CNS) involvement are excluded from clinical trials (21). Hence, no information from interventional clinical trials on activity of combined targeted therapy (BRAF and MEK inhibition) is available until present. Additionally, the pivotal study coBRIM has not included mM patients with brain metastases. Currently, there is one phase II trial (CONVERGE) for the treatment of brain metastases with vemurafenib and cobimetinib under investigation (22). The primary endpoint of this study is intracranial response. Radiological or stereo tactical treatment of brain metastases is only allowed prior to treatment start. CONVERGE evaluates the efficacy of vemurafenib and cobimetinib in brain metastases in a highly controlled setting.

Cobimetinib is approved for use in combination with vemurafenib for the treatment of adult patients with unresectable or metastatic melanoma with a BRAF V600 mutation.

To date no data are available on effectiveness, safety and, utilization of cobimetinib / vemurafenib in patients with mM in daily clinical routine in Germany.

Research Question and Objectives

The aim of this multi-center, non-interventional study is to provide data on effectiveness

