6.2 STUDY RATIONALE

Commonly, mM patients with CNS involvement are excluded from clinical trials (21). Hence, no information from interventional clinical trials on activity of combined targeted therapy (BRAFi/MEKi) is available until present. Additionally, the pivotal study of combined vemurafenib and cobimetinib treatment coBRIM has not included mM patients with brain metastases. Currently, there is one phase II trial (CONVERGE) for

the treatment of brain metastases with vemurafenib and cobimetinib under investigation (22). The primary endpoint of this study is intracranial response. Radiological or stereotactical treatment of brain metastases is only allowed prior to treatment start. CONVERCE evaluates the efficacy of vemurafenib and cobimetinib in brain metastases in a highly controlled setting.

To date no data are available on effectiveness, safety and, utilization of cobimetinib / vemurafenib in patients with mM in daily clinical routine in Germany

For information on the condition under observation please refer to the most recent version of the SmPC.

For information on vemurafenib /cobimetinib please refer to the most recent version of the SmPCs.

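### As written, intracranial ORR can count a CR or PR recorded after on-treatment brain surgery or radiotherapy, and the listed data items would not let the two be told apart

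*Protocol*

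**What the plan says.** Section 7.2 lists "Intracranial ORR (iORR" among the intermediate endpoints to be estimated, without a definition. The operative rule is in Section 8.7.2: "OR is defined as a complete or a partial response documentation on the basis of investigator assessment". It has no exception for locally treated lesions.

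The response item in Section 8.4.2 is a single entry, "Tumor Response (CR, PR, SD, PD) according to clinical practice". Neither that section nor Appendix 2 splits it into intracranial and extracranial response or gives it a date of its own.

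Local treatment of brain metastases during therapy is a listed data item, "Concomitant local treatment for brain metastasis (if appl". Its details, repeated in Appendix 2 note f, are the kind of treatment, the kind of radiotherapy, dose and fractionation, the number of lesions treated and steroid use. In the objectives these data appear only under utilization ("concomitant radiotherapy or surgery, type of radiotherapy").

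The background expects such treatment. For limited brain metastases it reports the guideline position as "For the latter, surgery or stereotactic radiotherapy is recommended". It also describes a phase II trial of the same combination, with intracranial response as primary endpoint, in which "Radiological or stereo tactical treatment of brain metastases is only allowed prior to treatment start".

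**The concern.** The stated aim is to provide data on the effectiveness of the drug combination. If a lesion is resected or irradiated after the drugs are started and a CR or PR is then documented, the rule in Section 8.7.2 counts it. The resulting iORR mixes drug response with the effect of local treatment, and the reader cannot see in what proportion.

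The analysis is descriptive and has no control arm, so no test is at risk. What is at stake is the meaning of a named effectiveness endpoint in the cohort with brain metastases. Data collection adds to the problem. An SAP could define how post-local-treatment responses are handled, but it could not recover dates that were never collected. Neighbouring items in Section 8.4.2 name their dates explicitly (treatment interruption, dose modification, progression, death, end of therapy). The local-treatment item and the response item do not.

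**Working it through.** The protocol states no expected iORR and no sample size or precision for it, so there is no figure to reproduce. The check has two parts.

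**1. Reading the rule against the data items.**
- Response rule (8.7.2): any documented CR or PR, without exception.
- Response criterion (8.4.2, Appendix 2 note g): clinical practice. No external criterion is named that would set aside irradiated or resected lesions.
- Local treatment during therapy (8.4.2, Appendix 2 note f): expected and recorded, undated in the item list.
- Use of those data (7.2): descriptive utilization only.
- General safeguard (8.9): confounding is listed and a sensitivity analysis is promised, but it is not specified and not tied to iORR or local treatment.

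Taken together, a CR or PR after local treatment is countable, and no stated analysis separates it.

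**2. Illustration of size.** Let p be the iORR without local treatment, f the share of Cohort B given local brain treatment during therapy, and q the chance that this turns a non-responder into a recorded CR or PR. Then

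counted iORR = p + (1 − p) × f × q.

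Inputs: n = 68 for Cohort B (Section 8.5). p = 16% is the only intracranial ORR in the protocol (Section 6.1, the vemurafenib monotherapy pilot study). p = 50% is an assumed contrast. **f and q are assumptions**; the protocol gives neither.

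| p | f | q | Excess (1 − p)fq | Counted iORR | Extra responders of 68 |
|---|---|---|---|---|---|
| 16% | 10% | 30% | 0.84 × 0.03 = 2.5 points | 18.5% | 1.7 |
| 16% | 25% | 50% | 0.84 × 0.125 = 10.5 points | 26.5% | 7.1 |
| 16% | 50% | 70% | 0.84 × 0.35 = 29.4 points | 45.4% | 20.0 |
| 50% | 10% | 30% | 0.50 × 0.03 = 1.5 points | 51.5% | 1.0 |
| 50% | 50% | 70% | 0.50 × 0.35 = 17.5 points | 67.5% | 11.9 |

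For scale, 11 of 68 responders (16.2%) has an exact 95% CI of 8.4% to 27.1%. The middle case therefore shifts the estimate by about as much as the upper arm of that interval (27.1 − 16.2 = 10.9 points).

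The excess is never negative: under a rule that counts any documented CR or PR, local treatment can add a response but cannot remove one already recorded. This assumes that local treatment does not prevent a later drug response from being documented.

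**The case against.** The best defence is that this is a real-world study. Drugs and local treatment are given together in practice, and response regardless of local treatment is a legitimate quantity to report. The protocol sets itself against a trial in a highly controlled setting where "treatment of brain metastases is only allowed prior to treatment start", so a different handling may be deliberate. That stands, and it is why the overall iORR should be kept. But the protocol never says that this is the intended quantity, and it presents its results as effectiveness of the drug combination.

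It can also be said that handling of a secondary descriptive rate belongs in an SAP, that the rule is being read from silence, and that the list of local-treatment details is introduced as non-exhaustive, so the eCRF may hold dates. Visit dates might also stand in for a response date. These points limit the finding to what the text permits. They do not remove it, because the items that an SAP would need are not listed.

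Three stronger readings are tempting and are not supported:
- A reader might infer that iORR *will* credit local treatment to the drugs. That depends on how many patients receive it during therapy, which is unknown.
- A reader might infer from the 16% that the rate would be more than doubled. With p = 16%, doubling needs f × q of at least 0.16/0.84 = 0.19, towards the upper end of the assumed ranges; with p = 50% it would need f × q = 1. The 16% is also a monotherapy result in previously treated, unresectable, corticosteroid-requiring brain metastases, so it is not a like-for-like benchmark for Cohort B however iORR is defined.
- A reader might infer that the design rests on this endpoint. Both cohorts were sized on median OS.

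**Conclusion.** The point holds in a limited form. The response rule in Section 8.7.2 permits an intracranial CR or PR recorded after on-treatment surgery or radiotherapy to count towards iORR, and nothing in the protocol connects the recorded local treatment to that endpoint. As an estimate of the drug-attributable rate, the resulting figure is biased upward. The amount cannot be derived from the protocol; the illustrated 1.5 to 29.4 points rests on assumed values of f, q and p. The generic sensitivity analysis in Section 8.9 does not resolve this. The part most in need of early correction is data collection, since missing dates and an unsplit response item cannot be repaired at the analysis stage. The consequence is for the interpretation of a secondary endpoint only.

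**What to change.** **Section 8.7.2.** Define iORR and keep the overall rate, labelled as response regardless of local brain treatment. Add a sensitivity analysis in which a Cohort B intracranial response first documented after the start of on-treatment local brain therapy counts as non-response, with all Cohort B patients kept in the denominator. Report the number locally treated. Any split of iORR by on-treatment local therapy should be marked as descriptive only: it conditions on a post-baseline event, and if patients failing in the brain are the ones sent for local therapy, the untreated group is selected and its rate may look too good.

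**Section 8.4.2 and Appendix 2 (notes f and g).** Add the date of local brain treatment, the date of response, and separate intracranial and extracranial response entries, each where available from routine records. A local-treatment date alone would not be enough, because response could still not be placed before or after it.

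**Cost.** A few eCRF fields and one additional analysis; no extra procedure for patients and no change to how they are treated. The sensitivity rate may be lower than the overall rate, since it discards responses that the drugs might have produced anyway, and with about 68 patients it will be imprecise.
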